4.4.2.1.2. Study Insulin Dose Analysis

For the study basal insulin dose, both average daily and weekly basal doses between visits in the treatment period for individual participants will be analyzed.

In the LY3209590 group,

- the average weekly dose of each visit (that is, average of weekly doses since the last visit) will be used as the average weekly basal dose, and
- the average daily basal dose will be the average weekly basal dose divided by 7.

For the insulin degludec group,

- the average daily basal dose since the last visit will be computed for each visit, and
- the average weekly basal dose will be calculated as the average daily basal dose multiplied by 7.

For all participants (with the exception of those treated with prestudy basal insulin glargine U-300), the average prestudy basal daily dose during the screening/lead-in period will be the baseline daily basal dose. For participants using prestudy glargine U-300, the average prestudy basal daily dose during the screening/lead-in period, multiplied by 0.8, will be the baseline daily basal dose. The baseline daily basal dose multiplied by 7 will be the baseline weekly basal dose.

The average bolus insulin dose of morning meal, midday meal, evening meal, and daily sum of additional doses between visits will be calculated for individual participants. Then the sum of averages of each visit for individual participants will be the average daily bolus dose. On the first day of study basal insulin (either LY3209590 or insulin degludec), a participant may use both prestudy bolus insulin and study-provided insulin lispro. Therefore, Week 0 (the first day of study basal insulin) will be excluded from the analysis of bolus insulin dose. The average weekly bolus dose is the average daily bolus dose multiplied by 7.

The average weekly total insulin dose is the sum of the average weekly basal dose and average weekly bolus dose. The average daily total insulin dose is the average weekly total insulin dose divided by 7.

The basal/total insulin dose ratio at each visit is the ratio of the average weekly basal dose and the average weekly total insulin dose.

If either weekly basal dose or weekly bolus dose is missing, the average weekly (or daily) total insulin dose and the basal/total insulin dose ratio will be set as missing for the analysis.

The insulin dose analysis will be conducted for

- both daily dose and weekly dose in units for each of the basal, bolus, and total insulin, respectively.
- dose in U/kg/day for basal, bolus, and total insulin, respectively, and
- basal/total insulin dose ratio.

4.4.2.1.3. Analysis of Fasting Blood Glucose

The analysis of fasting blood glucose (FBG), measured by SMBG, will be analyzed (in both CN and SI units). If a subject does not indicate which BG measurement was fasting, the FBG value will be assigned programmatically by designating the FBG as the first measurement between 5am-10am. These programmatically derived FBG values will also be included in the analysis.

4.4.2.2. Other Safety Endpoints

The safety measures based on CGM data will be analyzed as described in Section 4.4.2.1.1. For other safety measures, the details are provided in Section 4.6.

4.4.2.3. Patient Reported Outcome

The analyses for patient-reported outcomes will be based on the EAS2 data.

4.4.2.3.1. Diabetes Treatment Satisfaction Questionnaire

Diabetes Treatment Satisfaction Questionnaire-Status

The Diabetes Treatment Satisfaction Questionnaire-Status Version (DTSQs) (Bradley and Lewis 1990; Bradley 1994) is a diabetes-specific patient-reported outcome instrument that assesses the overall treatment satisfaction and perceived frequency of hyperglycemia and hypoglycemia. It is appropriate for use in both T1D and Type 2 diabetes mellitus. The DTSQs consists of 8 items that assess treatment satisfaction as well as concerns about hyperglycemia and hypoglycemia over the previous few weeks prior to the visit. Each item is rated on a 7-point Likert scale. Items 1 and 4 through 8 are rated from 0 (very dissatisfied) to 6 (very satisfied) and can be summed up to produce a treatment satisfaction score ranging from 0 to 36. Items 2 and 3 are scored individually, evaluate the perceived frequency of hyperglycemia and hypoglycemia, and are rated from 0 (none of the time) to 6 (most of the time).

The collection of the DTSQs is planned prior to the initiation of study treatment. The total scores of Items 1 and 4 through 8 and the individual scores of Items 2 and 3 will be summarized. A Wilcoxon rank-sum test will be used for treatment comparison.

Diabetes Treatment Satisfaction Questionnaire-Change

The Diabetes Treatment Satisfaction Questionnaire-Change Version (DTSQc) (Bradley 1999) was designed to overcome potential ceiling effects in the status version. The DTSQc has the same 8 items as the status version but is reworded slightly to measure the change in treatment satisfaction rather than absolute treatment satisfaction. Each item is scored on a scale of -3 to +3. For all items except Item 2 (perceived frequency of hyperglycemia) and Item 3 (perceived frequency of hypoglycemia), the higher the score, the greater the improvement in treatment satisfaction. A score of 0 represents no change. For Items 2 and 3, the lower the score, the better

the perception. The ratings for Items 1 and 4 through 8 are summed to obtain a total treatment satisfaction score ranging from -18 to 18. Items 2 and 3 are scored individually.

The collection of the DTSQc is planned after the initiation of study treatment. The total scores of Items 1 and 4 through 8 and the individual scores of Items 2 and 3 will be summarized. A Wilcoxon rank-sum test will be used for treatment comparison.

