1.1. Objectives, Endpoints, and Estimands

Objectives	Endpoints
Primary	

 To demonstrate that LY3209590 is noninferior to insulin degludec for the treatment of T1D in adults 	
 Change in HbA1c from baseline to Week 26
Key Secondary (Multiplicity Adjusted)	

 To demonstrate superiority of LY3209590 to insulin degludec 	
 Change in HbA1c from baseline to Week 26 Time in glucose range between 70-180 mg/dL (3.9-10.0 mmol/L), inclusive, measured by CGM 4 weeks prior to Week 26 Event rate of participant-reported, clinically significant nocturnal hypoglycemia (<54 mg/dL [3.0 mmol/L] or severe) during the treatment phase up to Week 52
Other Secondary	

 To investigate the effect of LY3209590 compared with insulin degludec in additional parameters of glycemic control 	
 Change in HbA1c from baseline to Week 52 Change from baseline to Weeks 26 and 52 in fasting glucose as measured by SMBG Glucose variability, measured by CGM 4 weeks prior to Weeks 26 and 52

Objectives	Endpoints
	
 • Time in glucose range between 70-180 mg/dL (3.9-10.0 mmol/L), inclusive, measured by CGM 4 weeks prior to Week 52 • Insulin dose at Weeks 26 and 52 
 ◦ basal ◦ bolus ◦ total, and ◦ basal/total insulin dose ratio

 • To compare the safety of LY3209590 to insulin degludec 	
 • Rate of composite of Level 2 and 3 hypoglycemia events during the treatment period • Body weight change from baseline to Weeks 26 and 52 • Time in hypoglycemia range with glucose <54 mg/dL (3.0 mmol/L), measured by CGM 4 weeks prior to Weeks 26 and 52 • Time in hyperglycemia range, defined as glucose >180 mg/dL (10.0 mmol/L), measured by CGM 4 weeks prior to Weeks 26 and 52

 • To compare treatment satisfaction and health-related quality of life between LY3209590 and degludec as assessed by patient-reported outcome questionnaires 	
 • DTSQ change from baseline to Weeks 26 and 52 • Change in SF-36 v2 acute form domain scores from baseline to Weeks 26 and 52
Tertiary	

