2.1. Multiplicity Adjustment

A graphical approach (Bretz et al. 2009, 2011) for multiple comparisons will be used to ensure the strong control of the overall type 1 error rate for testing the primary and key secondary (multiplicity adjusted) objectives. The overall significance level (α) will be set to 0.05. The total α will be used for the primary objective first, then the α will be allocated and transitioned to other key secondary objectives once the primary objective is met. Therefore, the noninferiority test for the primary objective will be based on the 2-sided 95% CI. Once the upper limit of the 2-sided 95% CI is below the NIM, the noninferiority will be achieved, and the α of 0.05 will be distributed to test superiority for the key secondary objectives. If the p-value of the 2-sided test for one of the key secondary objectives is below the assigned α level, the superiority is demonstrated, and the assigned α level will be distributed to the remaining objectives. The iterative test procedure continues until none of the remaining objectives can be demonstrated with their preserved α or all objectives are demonstrated successful. The NIM of 0.4% (for the treatment regimen estimand) and 0.3% (for the efficacy estimand) will both be tested to meet different regulatory requirements. No multiplicity adjustments will be made for conducting separate analyses relative to the efficacy and treatment regimen estimands. Each estimand will have its own familywise error rate of 0.05.

For primary and key secondary efficacy objectives, the details of the type 1 error control strategy are illustrated in [Figure BDCY.2.1](#). No multiplicity adjustments will be made for evaluating other secondary and exploratory objectives, or for safety assessments.

[figure not shown]

Figure BDCY.2.1. Type 1 error control strategy for primary and key secondary efficacy endpoints.

3. Analysis Sets

The following analysis populations and datasets are defined for the purpose of analysis.

Analysis Populations/ Datasets	Description
Entered Population	All participants who sign the informed consent form.
Randomized Population	All randomized participants. Participants will be analyzed according to the treatment they were assigned.
Modified Intent-to-Treat (mITT) Population	All randomized participants who took at least 1 dose of LY3209590 or insulin degludec. Participants will be analyzed according to the treatment they were assigned.

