4.4.2.3.2. Short-Form-36 Health Survey Version 2, Acute Form

Per copyright owner, the QualityMetric Health Outcomes™ Scoring (PRO_CoRe Version 2.0) Software will be used to derive the following domains:

- Physical Functioning domain
- Role-Physical domain
- Bodily Pain domain
- General Health domain
- Vitality domain
- Social Functioning domain
- Role-Emotional domain, and
- Mental Health domain.

Component summary scores

- Mental Component score, and
- Physical Component score.

Each domain is scored individually, and information from these 8 domains is further aggregated into 2 health component summary scores, the Physical Component Summary and Mental Component Summary. Scoring of each domain and both summary scores are norm-based and presented in the form of T-scores, with a mean of 50 and SD of 10. Higher scores indicate better levels of function and/or better health (Maruish 2011).

Summary statistics for the component summary scores and scores in each domain will be provided by study treatment. The scores at scheduled visits and the change from baseline will be analyzed by the MMRM model similar to the other efficacy endpoints (see Section 4.4.2.1). The last non-missing postbaseline observations will be analyzed by an ANCOVA model using the independent variables of treatment, strata (country, baseline HbA1c stratum [$<8.0\%$, $\geq 8.0\%$], CGM use prior to study entry [yes/no], and carbohydrate counting for prandial insulin dosing [yes/no]), and baseline value of the dependent variable as independent variables.

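### The DTSQc total score is given only an unadjusted Wilcoxon test, with no prespecified between-arm estimate or confidence interval

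*SAP*

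**What the plan says.** SAP Section 1.1 lists "DTSQ change from baseline to Weeks 26 and 52" as an Other Secondary endpoint, under the same objective as SF-36. Section 2.1 leaves it outside the testing scheme: "No multiplicity adjustments will be made for evaluating other secondary and exploratory objectives, or for safety assessments".

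Two forms of the questionnaire are used (Section 4.4.2.3.1). For the status form, "The collection of the DTSQs is planned prior to the initiation of study treatment"; for the change form, "The collection of the DTSQc is planned after the initiation of study treatment". On the change form, the six satisfaction items "are summed to obtain a total treatment satisfaction score ranging from -18 to 18", while Items 2 and 3 stand alone, each from -3 to +3.

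The planned analysis is the same for both forms: "The total scores of Items 1 and 4 through 8 and the individual scores of Items 2 and 3 will be summarized", and then "A Wilcoxon rank-sum test will be used for treatment comparison". The section names no covariate, stratum, between-arm estimate or interval.

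SF-36 (Section 4.4.2.3.2) gets an MMRM, and an ANCOVA with treatment, country, HbA1c stratum, prior CGM use, carbohydrate counting and the "baseline value of the dependent variable as independent variables". EQ-5D-5L, which is only tertiary, gets the same (Section 4.4.2.3.3). The general rule in Section 4.1 for continuous outcomes is MMRM or ANCOVA, shown as a difference in LS means with its 95% CI and p-value.

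**The concern.** The objective is to compare treatment satisfaction between arms. A rank-test p-value says whether the arms differ. It does not say by how many points on a scale running from -18 to 18, or how uncertain that figure is. A reader can subtract the arm means, but no interval for the difference is prespecified.

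The baseline DTSQs score and four stratification factors are already collected. Baseline satisfaction is a natural covariate for later change in satisfaction, yet the plan uses it only in a separate between-arm comparison of its own. The sister questionnaire under the same objective is analysed with baseline and strata, and the SAP gives no reason for the difference. What is at stake is how informative a secondary result will be. The validity of the comparison is not in question.

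**Working it through.** **The plan's own figures.** The documents give no SD, effect size or power for DTSQ, so the only figures to reproduce are the completers and the HbA1c superiority power.
- Completers per arm: 670/2 × 0.85 = 284.75, against the stated 284.
- HbA1c power: SE = 1.1 × √(2/284) = 0.0923; 0.3/0.0923 − 1.96 = 1.29, giving 90.1% against the stated 90%. Both reproduce.

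**Does adjustment gain power over the planned test?** The comparator must be the Wilcoxon test. The usual factor 1/(1−R²) compares ANCOVA with an unadjusted t-test, so it does not answer the question alone.

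Assumptions, none of them in the documents:
- R², the share of DTSQc variance explained by baseline DTSQs and strata, lies between 0 and 0.30.
- The effect gives an unadjusted t-test 80% power: (1.960 + 0.842) × √(2/284) = 0.235 SD.
- Under normality the Wilcoxon test has efficiency 3/π = 0.955 relative to the t-test.

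Wilcoxon power: effective n = 284 × 0.955 = 271 per arm; 0.235/√(2/271) − 1.96 ≈ 0.78, giving 78.2%. ANCOVA power uses residual SD √(1−R²). The sample-size ratio is [1/(1−R²)]/(3/π).

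| R² | Wilcoxon | ANCOVA | Sample-size ratio |
|---|---|---|---|
| 0 | 78.2% | 80.0% | 1.05 |
| 0.05 | 78.2% | 82.0% | 1.10 |
| 0.10 | 78.2% | 84.0% | 1.16 |
| 0.20 | 78.2% | 87.9% | 1.31 |
| 0.30 | 78.2% | 91.8% | 1.50 |

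The gain runs from 80.0 − 78.2 ≈ 2 to 91.8 − 78.2 ≈ 14 points.

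**Does that survive the shape of the score?** I simulated 2,500 trials per setting with 284 per arm, integer scores clipped to -18 to 18, and one covariate (R² set on the underlying scale). Entries are power, Wilcoxon / ANCOVA.

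| R² | Near-normal, about 7% at +18 | About 26% at +18 | Strong left skew |
|---|---|---|---|
| 0 | 77.9 / 78.9 | 74.8 / 74.7 | 87.7 / 52.4 |
| 0.10 | 78.6 / 83.4 | 75.7 / 79.4 | 85.9 / 56.5 |
| 0.20 | 78.3 / 87.8 | 76.0 / 82.3 | 87.9 / 61.7 |
| 0.30 | 78.6 / 91.2 | 75.2 / 86.6 | 85.9 / 64.0 |

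The first two columns use a latent shift of 1.41 with SD 6. The third uses an assumed exponential tail with scale 6 and a shift of 1.0, so levels should be compared within that column only. With a heavy ceiling the gain is about 0 to 11 points (86.6 − 75.2 = 11.4). Under strong skew ANCOVA loses about 22 to 35 points (85.9 − 64.0; 87.7 − 52.4).

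**The case against.** The case for the plan as written is substantial.

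- *A rank test suits this score.* The total is bounded, built from Likert-type ratings and possibly skewed. Under strong skew the Wilcoxon test was clearly the more powerful. This stands, and it is why the test should be kept.
- *The SF-36 comparison is not like for like.* DTSQc has no baseline value of its own: each item already asks about change, and DTSQs has a different scale (0 to 36). This also stands. DTSQs is a related baseline covariate, not the baseline of the dependent variable. ANCOVA does not need the two to share a scale.
- *DTSQ is not the only patient-reported outcome given a Wilcoxon test.* Section 4.4.2.3.4 uses it for both Basal Insulin Experience questions. Those are single 5-point items, however, whereas the DTSQc total sums six. The same reasoning does support rank methods for DTSQc Items 2 and 3.
- *There is some effect information.* Arm summaries are planned, Section 4.1 allows a comparison to rest on a two-sided test alone, and the table specifications are in separate documents. So it would be too strong to say there is no effect estimate. What the SAP lacks is a prespecified between-arm estimate with an interval.

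Two further inferences fail. A reader might take the SAP's remark on ceiling effects as evidence that DTSQc depends on starting satisfaction. The remark concerns the status form, and a ceiling there could weaken DTSQs as a covariate. A reader might also fault the between-arm test of baseline DTSQs. SAP Appendix 1 tests baseline characteristics generally, and the practice does not affect the DTSQc result.

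**Conclusion.** The point holds as a minor gap. For the DTSQc total, the SAP prespecifies no between-arm estimate or CI and leaves the baseline DTSQs score and the strata unused. This departs, without a stated reason, from Section 4.1 and from the treatment of SF-36 and EQ-5D-5L. The finding rests on the text alone and needs no assumed correlation.

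A reader might go further and conclude that the Wilcoxon test wastes precision. The documents do not support that: they give neither the correlation nor the score distribution, and the working shows that the sign of the difference depends on both. Nor is the planned test invalid. In a randomised comparison the unadjusted Wilcoxon test is sound, and stratified randomisation tends to make it conservative. The endpoint is outside alpha control, and no primary or key secondary conclusion is affected, so the impact is low.

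**What to change.** In SAP Section 4.4.2.3.1:

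- Keep the Wilcoxon test for the DTSQc total.
- Add, at Weeks 26 and 52 separately, an ANCOVA of the DTSQc total with treatment, baseline DTSQs total and the stratification factors (country, HbA1c stratum, prior CGM use, carbohydrate counting). Report the adjusted difference with its 95% CI.
- For Items 2 and 3, which are single ordinal responses, stay with rank-based methods, optionally stratified.
- Name the visits at which the Wilcoxon test is applied, since this section does not.

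If the sponsor prefers to remain with ranks for the total as well, a Hodges-Lehmann shift with its CI and a stratified rank test would supply the missing estimate.

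The cost is SAP wording and a small amount of programming, with no new data, visits or participants. If the database is already locked, report the addition as a labelled supplementary analysis.

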4.4.2.3.2. Short-Form-36 Health Survey Version 2, Acute Form

Per copyright owner, the QualityMetric Health Outcomes™ Scoring (PRO_CoRe Version 2.0) Software will be used to derive the following domains:

- Physical Functioning domain
- Role-Physical domain
- Bodily Pain domain
- General Health domain
- Vitality domain
- Social Functioning domain
- Role-Emotional domain, and
- Mental Health domain.

Component summary scores

- Mental Component score, and
- Physical Component score.

Each domain is scored individually, and information from these 8 domains is further aggregated into 2 health component summary scores, the Physical Component Summary and Mental Component Summary. Scoring of each domain and both summary scores are norm-based and presented in the form of T-scores, with a mean of 50 and SD of 10. Higher scores indicate better levels of function and/or better health (Maruish 2011).

Summary statistics for the component summary scores and scores in each domain will be provided by study treatment. The scores at scheduled visits and the change from baseline will be analyzed by the MMRM model similar to the other efficacy endpoints (see Section 4.4.2.1). The last non-missing postbaseline observations will be analyzed by an ANCOVA model using the independent variables of treatment, strata (country, baseline HbA1c stratum [$<8.0\%$, $\geq 8.0\%$], CGM use prior to study entry [yes/no], and carbohydrate counting for prandial insulin dosing [yes/no]), and baseline value of the dependent variable as independent variables.

4.4.2.3.3. EQ-5D-5L

The European Quality of Life Questionnaire (EQ-5D-5L) (EuroQol 2019) is a standardized, 5-item, self-administered instrument for use as a measure of health outcome. It provides a simple descriptive profile and a single index value for health status that can be used in the clinical and economic evaluation of health care as well as population health surveys. The EQ-5D-5L assesses 5 dimensions of health:

- mobility
- selfcare
- usual activities

- pain/discomfort, and
- anxiety/depression.

The 5L version scores each dimension at 5 levels:

- no problems
- slight problems
- moderate problems
- severe problems, and
- unable to perform/extreme problems.

In addition to the health profile, a single health-state index value can be derived based on a formula that attaches weights to each of the levels in each dimension. This index value ranges between <0 (where 0 is a health state equivalent to death; negative values are valued as worse than dead) to 1 (perfect health).

The second part of the questionnaire consists of the EQ Visual Analog Scale (VAS), which records the respondent's self-rated health status. The participant rates his/her perceived health from 0 (the worst imaginable health) to 100 (the best imaginable health). In conjunction with the health state data, it provides a composite picture of the respondent's health status.

The frequency and proportion of each level for a given item will be summarized by study treatment for each scheduled visit. The EQ-5D-5L index, EQ VAS score, and their change from baseline will be analyzed by the MMRM model similar to the other efficacy endpoints (see Section 4.4.2.1). The last non-missing postbaseline observations will be analyzed by an ANCOVA model using the independent variables of treatment, strata (country, baseline HbA1c stratum [<8.0%, ≥8.0], CGM use prior to study entry [yes/no], and carbohydrate counting for prandial insulin dosing [yes/no]), and baseline value of the dependent variable as independent variables.

4.4.2.3.4. Basal Insulin Experience

Likelihood of incorporating into routine

This is a Lilly-developed, participant-completed question to understand the participant's likelihood of incorporating their study insulin into their diabetes management routine. The question is rated on a 5-point scale with responses ranging from "very unlikely" to "very likely."

The frequency and proportion of the responses will be summarized by study treatment using a Wilcoxon rank-sum test for treatment comparison.

Preference

This is a Lilly-developed, participant-completed question to understand the participant's preference for their prestudy or current study treatment. The question is rated on a 5-point scale with responses ranging from "strongly prefer the study insulin" to "strongly prefer my previous insulin." The question also includes a "not applicable" option for participants that stayed on the same insulin in the treatment phase.

The frequency and proportion of the responses will be summarized by study treatment using a Wilcoxon rank-sum test for treatment comparison.

